## 9 STATISTICAL CONSIDERATIONS

### 9.1 Primary Objective

Overall good to excellent photographic cosmetic of the treated compared to the untreated breast, 24 months after radiation in  $\geq$  70% of patients, when compared to baseline pre-radiation photographs (See Section 2.4 for data on baseline expected risk). Two year photographic cosmetic scores will be scored according to the EORTC and NCIC photographic assessment system. The primary analysis will be a one sample t-test. The null hypothesis will be that the true rate is good to excellent photographic breast cosmetic assessment in  $\leq$  70% of patients. The one sided alternative hypothesis is a good to excellent photographic breast cosmetic assessment in  $>$  70% of patients. Assuming the true rate is 80% (e.g. exact equivalence), a sample of 87 evaluable subjects will provide 80% power at the alpha = 0.1 significance level.

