## STUDY SUMMARY

Title	NOVEMBER (Novem- (9), BrEast Radiation), A Phase II trial of a 9 day course of whole breast radiotherapy for early stage breast cancer.
Short Title	NOVEMBER.
Protocol Number	IRB#103976
IND	N/A
Phase	Phase II
Design	Single arm non-inferiority trial
Study Duration	8 years (3 years enrollment, 5 years follow-up)
Study Center(s)	Single-center at Huntsman Cancer Institute
Objectives	
Primary objective will be to evaluate 24 month breast photographic cosmetic scores with 9 fraction hypofractionated radiation compared to published hypofractionation radiation.
 
Secondary objectives include evaluation of patient reported outcomes, radiation toxicities, disease recurrence, and cost effectiveness.

Number of Subjects	102 enrolled for at least 87 evaluable
Diagnosis and Main Eligibility Criteria	Stage 0-IIIB breast cancer in the setting of breast conservation. Exclusion: Prior RT, Recurrent setting, Node positive, NO chemo before RT, No pregnancy
Study Product, Dose, Route, Regimen	External Beam Radiation Therapy (EBRT)
Duration of administration	9 days of Radiation (11-14 calendar days)
Reference therapy	Study therapy will be compared with published phase III data on 15 day, & 16 day hypofractionation breast RT studies from the UK and Canada.
Statistical Methodology	The primary analysis will be a one sample t-test. The null hypothesis will be that the true rate is good to excellent photographic breast cosmetic assessment in $\leq 70\%$ of patients. The one sided alternative hypothesis is a good to excellent photographic breast cosmetic assessment in $> 70\%$ of patients. Assuming the true rate is 80% (e.g. exact equivalence), a sample of 87 evaluable subjects will provide 80% power at the alpha = 0.1 significance level.

[figure not shown]
Protocol name: NOVEMBER (Novem- (9), BrEast Radiation), A Phase II trial of a 9 day course of whole breast radiotherapy for

early stage breast cancer.

Version Date: 23NOV2021

Principal Investigator: [name]

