## 2.4 Photographic Cosmetic Assessment

The EORTC Breast Cosmetic Rating system is a blinded digital photographic method that has been utilized in prior radiation studies and shown to be reliable and valid in detecting effects of radiation morbidity. This method compares the radiated breast with the contralateral untreated side and evaluates: Size, shape, location of the areola/nipple, appearance of the surgical scar, skin pigmentation changes, presence of telangiectasia and a global cosmetic score based on all of the factors. Characteristics are graded on a four-point scale: 0, excellent or no difference; 1, good or small difference; 2, fair or moderate difference; and 3, poor or large difference. In the UK Start B analysis of more than 900 patients, the rate of good/excellent photographic cosmetic assessment was 80% at 2 years. In the NCIC analysis of over 1200 patients the 3 year rate of good/excellent cosmetic assessment was 77% (no 2 yr rate given). Based on the NCIC and UK start photographic assessment, we anticipate that our patients will have an overall good-excellent cosmetic score in  $\geq 70\%$  of patients, when compared to their baseline.

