### **3.2 Number of Patients**

87 Analyzable patients. Plan for 15% drop out rate, therefore plan to enroll 102 patients

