## 8 CRITERIA FOR EVALUATION AND ENDPOINT

### 8.1 Photographic Assessment

The primary outcome of this study is the overall photographic cosmetic outcome of 9 fraction radiation in NOVEMBER versus published hypofractionation radiation.

Cosmetic effects of radiation can include telangiectasia, breast fibrosis, scar retraction and skin pigmentation changes. As this is not a blinded study, cosmetic assessment will be blinded with digital photography reviewed by a 3 unbiased reviewers. Reviewers will include a radiation oncologist, surgeon and nurse.

Confidential bilateral digital photographs (excluding the face) will be taken with a digital camera:

Photo #1) Bilateral, standing, anterior photo to show both breasts with the arms at 45° from the body and

Photo #2) Unilateral, close up of treated area to show the surgical scar at 24 months post radiation.

Photographs will be captured of both breasts at the following time points:

- Before radiation (Post Lumpectomy and before Radiation)
- 24 months after the completion of radiation

Photographs of both breasts will be collected as above and reviewed by a blinded Central Adjudication Committee according to the modified EORTC Cosmetic Rating System. An on-line training module is available.

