#### 9.2.2 Radiation Toxicity:

Incidence of acute and late radiation complications based on CTCAE 4.0 toxicity. The proportion of patients with acute or late radiation complications, will be estimated. Any event longer than 3 months will be considered a late effect.

The Clinical Cancer Research (CCR) database or data warehouse (as applicable) will be utilized to identify comparison group patients. Fisher's Exact test will be used to compare the rate of toxicity of study participants and comparison groups.

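### The yes/no primary endpoint is assigned a one-sample t-test, which keeps the stated 10% one-sided alpha at 87 evaluable patients but exceeds it at 11 of the 16 sizes from 87 to 102 (maximum 13.1%)

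*Combined protocol and SAP*

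**What the plan says.** Section 9.1 and the Statistical Methodology row of the Study Summary set a null of at most 70% of patients with good or excellent photographic cosmesis, against a one-sided alternative above 70%. The named method is a t-test: "The primary analysis will be a one sample t-test". For a true rate of 80%, both places state that "a sample of 87 evaluable subjects will provide 80% power at the alpha = 0.1 significance level".

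The evaluable number is not fixed. The Study Summary gives "102 enrolled for at least 87 evaluable", and Section 3.2 says "Plan for 15% drop out rate, therefore plan to enroll 102 patients".

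On the data behind the endpoint, Section 2.4 says "Characteristics are graded on a four-point scale", and Section 8.1 says that "cosmetic assessment will be blinded with digital photography reviewed by a 3 unbiased reviewers". Section 9.2.2 names Fisher's exact test for the toxicity rates, but no section names a test for a proportion for the primary endpoint.

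**The concern.** A one-sample t-test is built for a mean. Applied to 0/1 data, it replaces the null variance 0.70 × 0.30 with the variance at the observed rate. That variance is smaller whenever the observed rate is above 70%, so the test is slightly too easy to pass. The t reference distribution (86 or more degrees of freedom here) only partly offsets this. The discreteness of the count adds a further error that no continuous reference distribution removes.

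This is a single-arm trial with one primary test against a fixed historical rate, and its one-sided alpha is already 0.10. If that alpha holds only at some evaluable numbers, the strength of the primary claim depends on how many patients happen to have a usable 24-month photograph.

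**Working it through.** **Inputs.** Null rate 0.70, alternative 0.80, one-sided alpha 0.10, 87 evaluable, power 80% (Section 9.1); at least 87 evaluable of 102 enrolled (Study Summary); 15% dropout (Section 3.2). Assumption: each patient contributes one good/excellent yes/no result, as hypotheses stated as rates imply.

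**Rules compared.** For each evaluable number n, find the smallest success count x that meets the rule, with p̂ = x/n:

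- t-test: (p̂ − 0.70) / √[p̂(1 − p̂)/(n − 1)] > t(0.90, n − 1)
- null-variance z-test: (p̂ − 0.70) / √(0.21/n) > 1.2816
- exact binomial: P(X ≥ x | n, 0.70) ≤ 0.10

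The true type I error of any rule is P(X ≥ x | n, 0.70), and its power is P(X ≥ x | n, 0.80).

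**The plan's own figure.** At n = 87 all three rules give x = 67. For the t-test, 67/87 = 0.7701, the standard error is 0.0454, and t = 1.545 against a critical value of 1.291. With 66, t = 1.270 and the rule fails. P(X ≥ 67 | 87, 0.70) = 0.0928 and P(X ≥ 67 | 87, 0.80) = 0.7994. The stated 87 patients, 80% power and alpha 0.1 are therefore reproduced.

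**All sizes from 87 to 102.**

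| n | t-test boundary | t-test alpha | Exact boundary | Exact alpha | Exact power |
|---|---|---|---|---|---|
| 87 | 67 | 9.3% | 67 | 9.3% | 79.9% |
| 88 | 67 | 12.6% | 68 | 8.2% | 78.3% |
| 89 | 68 | 11.3% | 69 | 7.3% | 76.7% |
| 90 | 69 | 10.1% | 70 | 6.5% | 75.0% |
| 91 | 70 | 9.0% | 70 | 9.0% | 80.8% |
| 92 | 70 | 12.2% | 71 | 8.0% | 79.3% |
| 93 | 71 | 10.9% | 72 | 7.1% | 77.7% |
| 94 | 72 | 9.8% | 72 | 9.8% | 83.1% |
| 95 | 72 | 13.1% | 73 | 8.7% | 81.7% |
| 96 | 73 | 11.8% | 74 | 7.8% | 80.2% |
| 97 | 74 | 10.6% | 75 | 6.9% | 78.7% |
| 98 | 75 | 9.5% | 75 | 9.5% | 83.8% |
| 99 | 75 | 12.6% | 76 | 8.5% | 82.5% |
| 100 | 76 | 11.4% | 77 | 7.6% | 81.1% |
| 101 | 77 | 10.2% | 78 | 6.7% | 79.7% |
| 102 | 78 | 9.2% | 78 | 9.2% | 84.5% |

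The t-test exceeds 10% at 11 of the 16 sizes, and at each of them its boundary is one patient below the exact one.

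**Source of the excess.** At n = 88, 92, 95 and 99 the t-test boundary is also one below the null-variance z-test boundary, so the cause is the use of the observed variance. At the other seven (89, 90, 93, 96, 97, 100, 101) the z-test has the same boundary as the t-test, so the cause is discreteness. The z-test therefore exceeds 10% at 7 of 16 sizes, with a maximum of 11.8%.

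**Averages.** If the evaluable number follows Binomial(102, 0.85), an assumption taken from the planned dropout:

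| Test | Average alpha | Average power at 80% |
|---|---|---|
| t-test | 11.0% | 82.4% |
| Null-variance z-test or mid-p | 9.9% | 80.7% |
| Exact binomial | 8.0% | 77.0% |

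The chance that the realised n is one where t-test alpha exceeds 10% is 74%. Conditional on at least 87 evaluable, which has probability 0.535 under this model, average t-test alpha is 10.7% and that chance is 66%. For assumed dropout of 5% to 20%, average t-test alpha stays between 10.9% and 11.2%.

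**A case where the verdict changes.** Take 67 of 88: p̂ = 0.7614 and the standard error is 0.0457. Then t = 1.343 against 1.291, so p = 0.091 and the trial succeeds. The null-variance z-test gives 0.0614/0.0489 = 1.256, p = 0.105. The exact test gives P(X ≥ 67 | 88, 0.70) = 0.126. The last two do not reject.

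**The case against.** The strongest reply is that the plan's stated alpha and power are right at its stated design point, and that t-test may be a slip of naming. The figures 87, 80% and 0.1 fit an exact binomial design. The average excess is about one percentage point, and some of the 11 exceedances are trivial (10.1% at 90, 10.2% at 101). Over Binomial(102, 0.85), the chance that the t-test and the exact test disagree is about 3% at a true rate of 70%, 7% at 75% and 5% at 80%. Seven of the 11 exceedances would also occur with the null-variance z-test, an accepted method that averages 9.9% alpha and 80.7% power, close to what the plan states. The exact test falls below 80% power at 8 of the 16 sizes. Finally, the unstated rule for combining three reviewers' scores could move the count by more than one patient.

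Much of this stands as a limit on size. The effect is small, and only four sizes are due to the t-test as such. Holding alpha at or below 10% at every n, and not only on average, is a choice of convention. It does not rescue the text: the t-test is what is written, in two places, and 87 is a minimum and not the analysis number. The t-test's extra power comes from exceeding the stated alpha. The combining rule is a separate gap that this correction does not close. The use of Fisher's exact test in Section 9.2.2 is weak support, since that is a comparison of two groups.

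**Conclusion.** The concern holds and should be fixed, although the effect is modest. The plan tests a proportion with a t-test. The stated 10% alpha holds at 87, 91, 94, 98 and 102 evaluable patients and is exceeded at the other 11 sizes the plan allows, by between 0.1 and 3.1 percentage points. One evaluable patient above the minimum moves the true alpha from 9.3% to 12.6%. The trial's conclusion changes only if the count lands exactly one below the exact boundary at one of those 11 sizes.

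The figures at each n rest on one yes/no result per patient. The averages also rest on an assumed binomial evaluable number, but change little for dropout between 5% and 20%. The sample size itself is not in question.

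**What to change.** In Section 9.1 and in the Study Summary, replace the t-test with an exact one-sided binomial test of the null that the rate is at most 0.70, at alpha 0.10, with the success boundary set at the realised evaluable number. State the boundary at the design point: at least 67 of 87, alpha 9.3%, power 79.9% at a true rate of 80%. The boundaries for 87 to 102 evaluable are, in order, 67, 68, 69, 70, 70, 71, 72, 72, 73, 74, 75, 75, 76, 77, 78, 78. State also that each patient contributes one good/excellent yes/no result. Make the change before the 24-month photographs are analysed, so that nobody later chooses between tests that can disagree.

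The change is one sentence in two places, with no new data and no change to the enrolment target. The real cost is power: over 87 to 102 evaluable, the exact test has alpha of 6.5% to 9.8% and power of 75.0% to 84.5%, lowest at 90. If the sponsor prefers average power near 80%, a null-variance z-test or mid-p test is defensible. The plan should then say that alpha is held on average and not at every n, because either test still exceeds 10% at 7 of the 16 sizes.

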### 9.2 Secondary Objectives

#### 9.2.1 Patient reported outcomes

An important secondary objective will be one of patient reported outcomes. We've chosen to use the validated Breast-Q breast conservation survey.

Physical well-being, psychosocial well-being, sexual well-being, satisfaction with breast, and satisfaction with overall outcome at 6 months and 24 months after radiation will be evaluated. Scores at 6 months and 24 months post-radiation (relative to pre-RT) will be summarized and compared to prior published data, utilizing a two-sample t-test with a two-sided alternative.

#### 9.2.2 Radiation Toxicity:

Incidence of acute and late radiation complications based on CTCAE 4.0 toxicity. The proportion of patients with acute or late radiation complications, will be estimated. Any event longer than 3 months will be considered a late effect.

The Clinical Cancer Research (CCR) database or data warehouse (as applicable) will be utilized to identify comparison group patients. Fisher's Exact test will be used to compare the rate of toxicity of study participants and comparison groups.

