### 1.2 Secondary Objectives and Endpoint

1.2.1 To evaluate Breast-Q Patient Reported Outcomes (PROs) compared to historical control in breast conservation.

1.2.2 To evaluate the incidence of acute and late radiation complications, based on CTCAE 4.0 toxicity.

1.2.3 To evaluate the local and local regional recurrence rate.

1.2.4 To compare the direct and indirect patient costs for radiation therapy compared to historical controls as well as quality adjusted life years, utilizing the Breast-Q Patient Reported Outcomes (PROs) and the EQ-5D.

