## 2.6 Cost Effectiveness

We hypothesize that a 9 fraction course will be more cost effective. Costs will be compared to 45 de-identified patients that were treated with a standard hypofractionated regimen of 19 treatments. Direct costs of medical care to each patient will be estimated using utilization information from HCI financial/claims data. Generalized linear models will then be used to model these costs as a function of treatment, time on study, and all available baseline patient characteristics to assess the extent to which estimated direct cost is impacted by the type of radiation dosing. Given the well-known fact that healthcare costs are typically highly skewed, regression models will employ the appropriate distribution and transformation link.

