### 9.2.3 Local and local regional recurrence rate:

The cumulative incidence of local and local regional recurrence will be estimated using the cumulative incidence function treating death as the competing risk. In addition, local and local regional recurrence free survival will be summarized using the Kaplan-Meier estimators. The Clinical Cancer Research (CCR) database or data warehouse (as applicable) will be utilized to identify comparison group patients. The Cox proportional hazards model may be used to compare recurrence of study participants and comparison groups. Follow up time will be censored at the time of a competing event.

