### 12.4.1 Adverse Events (AE)

An adverse event is the appearance or worsening of any undesirable sign, symptom, or medical condition occurring after starting the study treatment even if the event is not considered to be related to study treatment. For the purposes of this study, the terms toxicity and adverse event are used interchangeably. Medical conditions/diseases present before starting study treatment are only considered adverse events if they worsen after starting study treatment. Abnormal laboratory values or test results constitute adverse events only if they induce clinical signs or symptoms, are considered clinically significant, or require therapy. Events that occur  $\leq 3$  months after radiation will be considered early toxicities while events occurring or persisting  $\geq 6$  months will be considered late toxicities.

Adverse events will be recorded after the start of radiation therapy. All events, even grade 1 will be recorded. AEs recorded until year 3.

Information about all adverse events, whether volunteered by the subject, discovered by investigator questioning, or detected through physical examination, laboratory test or other means, will be collected and recorded and followed as appropriate.

The occurrence of adverse events should be sought by non-directive questioning of the patient at each visit or phone contact during the study. Adverse events also may be detected when they are volunteered by the patient during or between visits or through physical examination, laboratory test, or other assessments. As far as possible, each adverse event should be evaluated to determine:

1. the severity grade based on CTCAE v.4 (grade 1-5)
2. its relationship to the study treatment (definite, probable, possible, unlikely, not related)
3. its duration (start and end dates or if continuing at final exam)

4. action taken (no action taken; study treatment dosage adjusted/temporarily interrupted; study treatment permanently discontinued due to this adverse event; concomitant medication taken; non-drug therapy given; hospitalization/prolonged hospitalization)
5. whether it constitutes an SAE

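### The late-toxicity comparison with database patients uses an unadjusted Fisher's exact test on crude proportions, so unequal follow-up or recording can create or hide a difference

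*Combined protocol and SAP*

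**What the plan says.** Objective 1.2.2 is "To evaluate the incidence of acute and late radiation complications, based on CTCAE 4.0 toxicity"; it names no comparator. Section 9.2.2 begins with estimation: "The proportion of patients with acute or late radiation complications, will be estimated". It then says that the Clinical Cancer Research "database or data warehouse (as applicable) will be utilized to identify comparison group patients", and that Fisher's "Exact test will be used to compare the rate of toxicity of study participants and comparison groups". The section does not state who qualifies as a comparator, which schedule or calendar period they come from, how many there will be, the grade counted, or the time point.

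Other sections treat similar comparisons differently:
- Section 2.6 models cost "as a function of treatment, time on study, and all available baseline patient characteristics".
- Section 9.2.3, using the same database, says that recurrence "will be estimated using the cumulative incidence function treating death as the competing risk", and allows a Cox model for the comparison. It names no covariates.
- Section 8.4 case-matches only the 45-patient expense-survey cohort, on distance and employment.

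The definition of late toxicity also varies. Section 9.2.2 says "Any event longer than 3 months will be considered a late effect". Section 12.4.1 says that events up to 3 "months after radiation will be considered early toxicities while events occurring or persisting" to 6 months or more are late. The stopping rule in section 8.6 also uses 6 months or more.

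**The concern.** The comparators are not randomised, and the two groups are likely to differ in three ways that a 2x2 table cannot see.

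- **Time at risk.** Late toxicity accumulates. A group followed longer shows a higher crude proportion at the same underlying risk.
- **Recording.** Section 12.4.1 has trial patients questioned at each visit, with all grades recorded to year 3. Nothing says that database patients were graded this way.
- **Case mix.** Sections 4.1 and 4.2 restrict the trial to node-negative patients and exclude chemotherapy before radiation, prior chest radiation, active collagen vascular disease and significant post-lumpectomy complications. No such limits are stated for comparators.

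At stake is the only planned between-group test of toxicity. It could report a difference that does not exist or, more seriously for a new schedule, miss one that does.

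**Working it through.** The documents give no sample size, alpha or power for this comparison, so there is no stated figure to reproduce. The check shows how Fisher's test behaves when follow-up, recording or case mix differ.

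**Inputs from the documents.** Trial size is 102 enrolled (section 3.2). Expected grade 2 or higher non-acute toxicity is 7-10% (section 2.2); the upper end is used. Adverse events are recorded to year 3 (section 12.4.1).

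**Assumptions not in the documents.** Two-sided alpha 5%; 102 or 204 comparators; constant hazard; and the comparator follow-up, capture and case-mix values below.

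**Crude rates with no true schedule effect**
- Hazard: λ = −ln(0.90)/3 = 0.0351 per year.
- Comparators followed 5 years: 1 − exp(−5λ) = 16.1%.
- Comparators followed 1 year: 1 − exp(−λ) = 3.5%.
- Half of events charted over 3 years: 0.5 × 10% = 5.0%.
- 5 years and half charted: 0.5 × 16.1% = 8.05%.
- Case mix: a factor with relative risk 2, present in 20% of trial and 50% of database patients, gives 0.10/1.2 × 1.5 = 12.5%. Relative risk 3 gives 0.10/1.4 × 2 = 14.3%.

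**Rejection probability.** For two independent binomials, I summed the probability of every table in which the two-sided Fisher p-value is at most 0.05. The trial rate is 10% throughout.

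| Comparator situation | Comparator rate | Result | 102 comparators | 204 comparators |
|---|---|---|---|---|
| Like for like | 10% | trial better / trial worse | 1.5% / 1.5% | 1.8% / 2.1% |
| 5-year follow-up | 16.1% | trial better | 19.8% | 26.9% |
| 1-year follow-up | 3.5% | trial worse | 37% | 59% |
| Half of events charted | 5.0% | trial worse | 19.5% | 34.2% |
| 5 years and half charted | 8.05% | either direction | 4.7% | 7.7% |
| Case mix, relative risk 2 | 12.5% | either direction | 5.8% | 7.4% |
| Case mix, relative risk 3 | 14.3% | either direction | 11.2% | 14.9% |

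**Masking.** Suppose true toxicity is doubled in the trial (20% against 10% at 3 years). With equal follow-up the test detects this in 45% / 63% of cases. With 5-year comparator follow-up (16.1%) it does so in 8% / 12%.

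**Events available for adjustment.** 0.07 × 102 = 7.1 and 0.10 × 102 = 10.2, so about 7 to 10 late events in the trial arm.

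**The case against.** **The comparison has a limited role.** Objective 1.2.2 names no comparator, while objectives 1.2.1 and 1.2.4 do. No decision rests on this test: section 8.6 applies a fixed threshold (more than 20% against an expected 10% or less), and section 12.3 provides quarterly safety review. A reader might infer that this is the trial's main safety comparison, or that the protocol will attribute any difference to the schedule. The documents say neither. This stands, and it limits the weight of the point.

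**Trial follow-up does not simply end at year 3.** Section 3.4 and the study calendar plan a 5-year chart review that covers toxicity. If those data enter the proportion, the 3-versus-5-year contrast shrinks, and late trial events would also come partly from charts. This stands in part: section 9.2.2 does not say which follow-up is counted, and with a planned 15% dropout trial follow-up will itself vary.

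**Acute events are different.** A window of 3 months or less is short and fixed, so a crude proportion is reasonable as far as time at risk is concerned. This stands.

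**The scenarios are chosen and work one at a time.** Follow-up and under-recording can push in opposite directions, and combined at these values they give close to nominal rejection. Moderate case-mix imbalance has a modest effect. This stands as a limit on size. It is not a safeguard, because the cancellation depends on the values assumed.

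**Matching at selection is not excluded.** That is true, but it is not planned in the text either.

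**Conclusion.** The point holds for late toxicity. The stated method ignores time at risk and case mix in a non-randomised comparison, and no other section repairs this. Under the assumptions above, a single imbalance in follow-up or recording raises false rejection in one direction from about 2% to roughly 19-34% (higher still if comparators have only 1 year), and can hide most of the power to see a doubling. These figures show possible size, not expected bias, because comparator number, follow-up and recording are all unstated.

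The point does not extend to the primary cosmetic test, the stopping rule or, on follow-up grounds, acute toxicity. Nor do the documents support a claim that the comparison is biased in a known direction. It should be corrected before the analysis, as a secondary-endpoint issue.

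**What to change.** Amend section 9.2.2 as follows.

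1. **Comparator eligibility.** Restrict database patients to those who meet the trial's criteria: N0, no chemotherapy before radiation, standard hypofractionation with a boost, and a similar calendar period. Nodal status and boost belong here and not in a propensity model, because they are essentially constant in the trial arm (section 4.1; boost dose in section 5.3.3).
2. **One late-effect definition.** Reconcile section 9.2.2 (longer than 3 months) with section 12.4.1 (6 months or more), and use the same definition in both groups.
3. **Estimand.** Report late grade 2 or higher toxicity as cumulative incidence at 24 and 36 months, with death as a competing risk and censoring at last follow-up in both groups.
4. **Comparison.** Compare at those times with propensity weighting or matching on a few recorded factors that vary in both groups, such as age, stage and later chemotherapy. Limit it to grades recorded in both sources. With about 7 to 10 expected late events, the model must stay small.
5. **Fisher's test.** Keep it on crude proportions as description, or for acute events within the window of 3 months or less.

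The cost is SAP wording and modest extra analysis, with no new visits or trial patients. Intervals will be wider with so few events. Weighting cannot repair unequal charting, so that residual bias should be stated as a limitation.
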